#### Listing 16.2.6.2 CD4+ Cell Count (cells/mm^3)

# Unimputed Original Values Imputed with LOCF [5]

Treatment	Patient ID	Visit [1]	Visit Date (Study Day)	CD4+ Cell Count (cells/mm^3) [2]	CD4+ Cell Count Change from Baseline (%)	Toxicity [4]	CD4+ Cell Count (cells/mm^3) [2]	CD4+ Cell Count Change from Baseline (%)
C1:301/800mg	311-XX-XXX	XXXXXXX	DDMONYYYY (XX)	XXX*	XXXX	XXXX	XXX*	XXXX
C2:800mg	311-XX-XXX	XXXXXXX	DDMONYYYY (XX)	XXX	XXXX	XXXX	XXX	XXXX

[1] EOS=End of Study visit conducted at Week 174 (for TMB-301 rollovers)/Week 150 (for all other patients).

[2]\*=below 200 cells/mm^3

[3] Calculated as (visit value - baseline)/baseline\*100%

[4]Toxicity is defined as 2 consecutive laboratory results, at least 14 days apart, with a CD4+ cell count below 200 cells/mm3 that also represents a 50% reduction from the baseline CD4+ cell count.

[5] Missing values are imputed using the Last Observation Carried Forward (LOCF) method.e

Westat (Created on DDMMMYYYY)
S:\TMB311\DA\SAS\L\_CD4.SAS

#### At EOS

Treatment	Patient ID	Visit [1]	Visit Date (Study Day)			
				Virologic Outcome [2]	Virologic Failure [3]	Virologic Success [4]
C1:301/800mg	311-XX-XXX	XXXXXXX	DDMONYYYY (XX)	XX	XXXXXXX	XXXXXX
C2:800mg	311-XX-XXX	XXXXXXX	DDMONYYYY (XX)	XX	XXXXXXX	xxxxxx

[1] Visits are assigned based on study day using the windows defined in the statistical analysis plan.

[2] Per the Snapshot Approach:

1=Virologic success (=0.5 log copies/mL drop from Baseline in viral load)

2a=(<0.5 log copies/mL drop from Baseline in viral load)

2b=Discontinued because of virologic failure

2c=Discontinued because of other reasons and drop from baseline in viral load at the time of discontinuation was <0.5 log copies/mL

### 2d=OBR changed

## 3a=Discontinued because of AE or death

3b=Discontinued because of other reasons and drop from baseline in viral load at the time of discontinuation was >=0.5 log copies/mL

# 3c=Missing data during the window but on study

[3] Failure to achieve/maintain response=Patient does not have >=0.5 log10 decline from baseline(BL) by Week 12 on study drug OR patient has a 0.5 log10 decline from BL prior to Week 12 but fails to maintain the 0.5 log10 decline from BL with a <1 log10 increase from nadir on any two consecutive scheduled efficacy assessments after Week 12.

Rebound=Patient has a >=0.5 log10 decline from BL by Week 12 that is maintained but viral load remains >=50 copies (not suppressed), followed by >=1 log10 increase from nadir at two consecutive scheduled visits any time after the primary endpoint.

Breakthrough=Patient has suppressed viral load (< 50 copies) at any time after primary endpoint followed by >=200 copies at two consecutive scheduled efficacy assessments.

[4]Suboptimal Response=Patient has a 0.5 log10 decline but does not suppress (<50 copies) at any time after primary endpoint; Virologic Suppression=Patient has a 0.5 log10 decline and does suppress (<50 copies) at any time after primary endpoint

Programming note: See footnotes (values to the left of the =) to indicate what values will be displayed in the listing.

Westat (Created on DDMMMYYYY)
S:\TMB311\DA\SAS\L VLOUTCOMES.SAS

 For TMB301 Rollovers, BASELINE is the value recorded on Day 7 of the TMB-301 study. For TMB202 Rollovers, BASELINE is the value recorded on Day 0 of the TMB-202 study. Lab samples were not collected at the TMB-311 Screening for the Cohort 1 patients. EOS=End of Study visit conducted at Week 96.

 $\label{lem:westat} \begin{tabular}{ll} $\tt Created on DDMMYYYY) \\ {\tt S:\TMB311\DA\SAS\L\_LABOTH.SAS} \end{tabular}$ 

 L = Below lower limit of normal; H = Above upper limit of normal.

 Potentially Clinically Significant is defined as having a result either below the lower limit of normal or above the upper limit of normal.

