4.4 Missed Doses of Study Drug

4.4.1 Cohort 1

Patients should receive study drug per the Schedule of Events (Section 3.4). A missed dose is defined as any dose of study drug that is not administered within the study visit window. Patients who miss doses of study medication for two consecutive dosing intervals (i.e., >28 days without a study drug infusion) of 800 mg dosage or one and one-half dosing intervals (i.e., >42 days without a study drug infusion) of the 2,000 mg dose may be withdrawn from the study.

Missed Doses. If a dose is missed, the missed dose should be administered at the first opportunity. If an 800 mg dose is missed and cannot be administered at least 3 days before the next scheduled dose, it should be skipped. If a 2,000 mg dose is missed and cannot be administered at least 5 days before the next scheduled dose, it should be skipped.

End of study (EOS) procedures should be performed as soon as possible after the patient qualifies for withdrawal due to missed doses. Patients who are withdrawn from the study for missed doses may not be permitted to participate in other ibalizumab protocols.

4.4.2 Cohort 2

Patients should receive study drug per the Schedule of Events (Section 3.4). A missed dose is defined as any dose of study drug that is not administered within the study visit window. Patients who miss doses of study medication for two consecutive dosing intervals (i.e., >28 days without a study drug infusion) or miss greater than two doses cumulatively will be withdrawn from the study. EOS procedures should be performed as soon as possible after the patient qualifies for withdrawal due to missed doses. Patients who are withdrawn from the study for missed doses may not be permitted to participate in other ibalizumab protocols.

Missed Initial (Loading) Dose. If the initial 2,000 mg dose (loading dose) of study drug is administered outside the treatment window, the dose should be administered at the first available opportunity and the timing of subsequent doses should be adjusted to coincide with the actual administration time of the first dose.

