For Cohort 2, patients will complete all screening procedures during the six weeks before Baseline/Day 0. Successful screening results will allow the patients to proceed to the Baseline/ Day 0 Visit, where they will initiate the selected OBR in addition to undergoing physical and laboratory measures. At this visit patients will also receive the loading dose of the study medication (2000 mg). Patients will return to the clinic on Day 7 for effectiveness and safety evaluations, and on Day 14 and every two weeks thereafter through the remainder of participation in the study (up to 144 weeks) for study drug administration (800 mg) and effectiveness and safety evaluations. Patients who are discontinued or who withdraw from the study prematurely will be asked to return for an Early Withdrawal visit to have all assessments detailed in the Schedule of Events for that visit performed.

All patients who complete Week 144 or end of study (EOS) visit will return for a follow-up visit at Week 150. Patients may be discontinued from the study at the patient's request or if the patient becomes pregnant, at investigator request, for a protocol violation, for treatment-related serious or intolerable adverse events (AEs), for toxicity (defined as two consecutive laboratory results, at least 14 days apart, with a CD4+ T-cell count below 200 cells/mm3 that also represents a 50% reduction from the Baseline CD4+ T-cell count), or for virologic failure. Virologic failure is defined as two consecutive measurements beginning at Week 24 or later if less than a 0.5 log10 decline from the Baseline viral load.

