## 3.3. Data Handling

#### 3.3.1. Measurement Times

The nominal visit time point entered on the electronic case report forms (eCRFs) will be used. Patients are asked to adhere to the following visit schedule (with windows in parentheses):

- For Cohort 1 patients, Screening and Day 0 (first on-study administration of ibalizumab) are scheduled for the same day.
- For Cohort 2 patients, the Screening will occur 1 to 6 weeks prior to Day 0.
- For Cohort 2, Day 7 (+/- 1 day) serves as the time point at which the antiviral activity of ibalizumab will be assessed to address the primary effectiveness objective.
- For all Cohorts, Day 14 (+/- 1 day) and Week 4 (+/- 2 days) through Week 144/EOS Visit (+/- 2 days) from the Day 0 date (Visit Week will depend on the dosing schedule per Cohort 1 or 2; please refer to the Schedule of Visits Tables 3.1-3.6 in the study protocol).

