## 3.3.4. Missing Data Conventions

Cohort 2 patients with missing data at Day 0 will use the Screening visit value as their Day 0 result. Similarly, patients with missing data at Screening will use the Day 0 visit value as their Screening result. No Screening or Day 0 data will be imputed for Cohort 1 patients.

Unless otherwise specified, missing data for subsequent visits will be considered missing at random and will not be imputed. If necessary, imputation of partial dates may be performed during the data analysis and will be documented (e.g., missing month=July; missing day=15).

The **Missing Equals Failure (MEF)** imputation technique will be applied to the viral load measures (log10 copies/mL and copies/mL) only. If a viral load measurement is missing at any scheduled visit, the value will be replaced with the baseline viral load measurement. Also, all visits after a confirmed virologic failure will be imputed as failures (replaced with the baseline measurement) for all study visits even if the patient discontinued early.

The Last Observation Carried Forward (LOCF) imputation technique will be applied to the CD4+ T-Cell Counts (cells/mm^3) only. If a CD4+ T-Cell Count is missing at any scheduled visit, the value will be replaced with the most recent previous non-missing value.

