#### 4.5.2.1 HIV-1 RNA levels (copies/mL)

The frequency and proportion of patients achieving RNA levels < 50 copies/mL and < 400 copies/mL along with 95% confidence intervals around the observed rate will be presented at all key visits [Day 7 (Cohort 2 only), and Weeks 24, 48, 72, 96, 120, and 144/EOS] where assessed.

Summary statistics for the actual and change from Baseline of RNA levels will be presented for at all visits where assessed.

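### The SAP body sets end of study at the on-drug Week 144 visit, but listing footnotes and protocol text give other weeks and a second visit rule; this touches the 144/EOS viral-load row, the EOS listings and late withdrawals

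*SAP*

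**What the plan says.** **Week 144.** SAP 3.3.1 counts visits from TMB-311 Day 0 through a Week 144/EOS visit (±2 days). Protocol Tables 3-2, 3-4 and 3-6 have separate columns for 144/EOS, 150/Follow-up and Early Withdrawal. SAP 2.1 states: "All patients who complete Week 144 or end of study (EOS) visit will return for a follow-up visit at Week 150". SAP 4.5.2.1 reports at "key visits [Day 7 (Cohort 2 only), and Weeks 24, 48, 72, 96, 120, and 144/EOS] where assessed", and the later parts of 4.5.2 end on the same row.

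**Other weeks.**
- Footnote [1] of the SAP laboratory listing: "Lab samples were not collected at the TMB-311 Screening for the Cohort 1 patients. EOS=End of Study visit conducted at Week 96". Its first sentence conflicts with the combined Screening/Day 0 sampling in Protocol 6.1.1 and 6.2.1. That is a wording matter and not part of this point.
- Footnote [1] of SAP Listing 16.2.6.2 (CD4): "EOS=End of Study visit conducted at Week 174 (for TMB-301 rollovers)/Week 150 (for all other patients".
- Protocol 4.4.2 ties EOS procedures to Week 102, and Protocol 6.4 ties EOS to Week 96.
- Footnote 6 of Table 3-6 (Cohort 2) limits Early Withdrawal procedures to exits before Week 102. The matching Cohort 1 footnotes (Tables 3-2 and 3-4) say before Week 150.
- Protocol 6.3.7 is headed Week 150, but its first line calls the visit Week 102.

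**Visit rule.** SAP 3.3.1: "The nominal visit time point entered on the electronic case report forms (eCRFs) will be used". The EOS virologic-outcome listing: "Visits are assigned based on study day using the windows defined in the statistical analysis plan".

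**Missing viral load.** SAP 3.3.4: "If a viral load measurement is missing at any scheduled visit, the value will be replaced with the baseline viral load measurement".

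**The concern.** The 144/EOS row carries the longest-term viral-load results, so it should have one meaning. Week 144 is measured on drug and Week 150 off drug, and a footnote that calls Week 150 the EOS visit invites mixing the two. With two visit rules, a table and a listing can disagree about whether the same patient has a Week 144 value. Read literally, the Week 96 and Week 102 cut-offs also excuse later leavers from the withdrawal visit, although those are patients whose last on-study sample matters. Finally, MEF scores anyone without a Week 144 value as a non-responder, including a suppressed patient who leaves because ibalizumab has become commercially available, which the protocol lists as a reason to stop.

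**Working it through.** **1. The labels against Week 144.**

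| Week | Where | Offset from 144 |
|---|---|---|
| 96 | SAP laboratory listing; Protocol 6.4 | −48 |
| 102 | Protocol 4.4.2; Table 3-6 footnote 6 | −42 |
| 150 | SAP CD4 listing | +6 |
| 174 | SAP CD4 listing, TMB-301 rollovers | +30 |

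The current schedule has 144 + 6 = 150. Likewise 96 + 6 = 102, so 96 and 102 look like the EOS and follow-up weeks of a shorter schedule. TMB-301 ran from a Day 7 baseline to Week 25, or 25 − 1 = 24 weeks, and 150 + 24 = 174. So 150 and 174 are probably one follow-up visit on two clocks. Both readings are inferences.

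**2. Why Week 144 and Week 150 must not share a label.** No drug is given at Week 150. The interval is 6 × 7 × 24 = 1,008 hours. Protocol 1.3 gives half-lives of 75 and 79 hours from an earlier intravenous study: 1,008/79 = 12.8 and 1,008/75 = 13.4 half-lives. The residual is 2^−12.8 to 2^−13.4, about 0.014% to 0.009%, assuming no ibalizumab after Week 144. Week 150 is therefore an off-drug measurement.

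**3. Nominal visit against study day.** Under Protocol 4.4.2, a Cohort 2 dose given more than 7 but less than 14 days late is a reload that takes the place of the next visit, and later visits are re-timed from it. If the delay is L days, later visits shift by L − 14 days, which is −6 to −1 for L = 8 to 13. In the protocol's example, Day 49 is missed and the reload is given on Day 58, so L = 9. The next dose is on Day 72 instead of Day 77, a shift of −5.
- Week 144 on the Day 0 clock: 144 × 7 = Day 1008; with ±2 days, Days 1006 to 1010.
- Shifted Week 144: 1008 − 5 = Day 1003; with ±2 days, Days 1001 to 1005.

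The ranges do not overlap. The value counts under the nominal rule. Under a study-day window the patient would be in snapshot category 3c, on study with missing data. This treats the ±2-day scheduling tolerance as the window, because the SAP gives no other, and assumes one such episode with no later re-timing.

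**4. Early Withdrawal cut-offs.** Protocol 6.4 leaves out exits from Week 96 to Week 144: 144 − 96 = 48 weeks, or 48/144 = 33% of the schedule. Table 3-6 footnote 6 leaves out Week 102 onward: 144 − 102 = 42 weeks. As an example, take a Cohort 2 patient who leaves at Week 118 without a withdrawal visit. The last scheduled viral load is Week 108, 10 weeks earlier. The last scheduled hematology and chemistry is Week 96, 22 weeks earlier.

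**5. Effect of MEF at Week 144.** Let q be the share of patients with a Week 144 value and p the response among them. MEF reports p × q. The documents give neither figure. Assuming p = 60%:
- q = 70%: 0.60 × 0.70 = 42%
- q = 50%: 0.60 × 0.50 = 30%
- q = 30%: 0.60 × 0.30 = 18%

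The same observed response can thus appear as anything from 42% to 18%, depending only on how many patients remain. The observed n and proportion are needed to read the row.

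**The case against.** The strongest reply is that this is editorial. The SAP body writes 144/EOS throughout, fixes the clock at TMB-311 Day 0, and keeps Week 150 and Early Withdrawal apart. The stray SAP weeks sit in mock-listing footnotes, and the programming notes say that visit names in the shells are examples to be corrected. The CD4 and virologic-outcome listings print the visit date and study day, so a wrong footnote alters no number. The study is descriptive, with no formal testing planned.

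Most of this stands, and it rules out several stronger readings that a reader might infer:

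- *Five competing definitions of EOS.* Not supported: Week 144 is the only one the SAP's analysis sections use.
- *The row is each patient's own last visit.* Not supported: MEF applies at scheduled visits, and the snapshot categories classify patients who have already discontinued, so both assume a fixed visit.
- *Missed-dose withdrawals enter the EOS row.* Protocol 4.4.1 and 4.4.2 call for EOS procedures at withdrawal but do not say the visit is recorded as EOS. Other sections send withdrawals to an Early Withdrawal visit, and no eCRF is shown.
- *CD4 and virologic outcome shift as much as viral load.* CD4 uses LOCF, so an early leaver's last value is carried forward. In the snapshot, a responder who leaves for other reasons falls in category 3b, apart from the failure categories.
- *Dropout can be applied to the TMB-301 Week 25 figure of 43% below 50 copies/mL.* The reported 43% and 50% fit 17/40 and 20/40, and 50% is impossible with 31 completers. The nine non-completers are very likely already in the denominator, so this would discount them twice.
- *The Week 120-to-150 gap in hematology and chemistry is an EOS error.* It is a feature of the schedule.

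Three things survive as more than clerical: the two visit rules genuinely conflict, the Early Withdrawal cut-offs exclude late leavers as written, and MEF alone is hard to interpret at Week 144.

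**Conclusion.** The point holds in limited form. The intended EOS is the on-drug Week 144 visit, but current text contradicts it in two SAP listing footnotes and in Protocol 4.4.2 and 6.4. Table 3-6 footnote 6 carries an outdated withdrawal cut-off, and one SAP listing uses a different visit rule from SAP 3.3.1.

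The reach is the last row of the secondary viral-load tables, the EOS listings, and Early Withdrawal data after Week 96 or 102. Day 7 efficacy, fixed visits through Week 120 and, because of LOCF, most CD4 results are unaffected. Other protocol text (5.3.2 and 6.3) asks for a withdrawal visit at any premature exit, so the lost data are a risk rather than a certainty. The number of patients affected cannot be derived: rates of leaving before Week 144 and of reload-shifted schedules are not given. The 18% to 42% range shows how MEF works; it is not a forecast.

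**What to change.** 1. In SAP 3.3.1, define EOS as the nominal Week 144 visit, with weeks counted from TMB-311 Day 0 in all groups, and use this in every table and listing.
2. Report Week 150 as Follow-up (off drug). Report every earlier exit, including missed-dose withdrawals, as Early Withdrawal.
3. Apply the nominal-visit rule to the EOS virologic-outcome listing and correct its footnote.
4. Correct the EOS footnotes on the laboratory and CD4 listings. Hematology, chemistry, hepatitis serology and CRP are not scheduled at Week 144, so the laboratory footnote should say so. It should name Week 120 as the last scheduled on-drug hematology and chemistry.
5. Correct Protocol 4.4.2, 6.3.7 and 6.4 and Table 3-6 footnote 6, so that Early Withdrawal procedures apply to any exit before Week 144/150.
6. Beside the MEF result, show the observed n and proportion at Week 144. Protocol 9.2.1.2 already foresees a supportive analysis without imputation, but SAP 3.2.1 makes the mITT analysis conditional and does not carry that feature over.

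The cost is SAP wording, relabelled shells, one extra column and short protocol corrections. No new kinds of sample are needed; late leavers would have the withdrawal visit that Protocol 5.3.2 already asks for.
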